**Evaluations**

These evaluation measurements will be administered at the initial research assessment session as well as the final research assessment session, except the K-SADS and WASI which will be only administered at the initial research assessment session. A separate remote visit may be used to conduct K-SADS administration. All of these evaluations are solely performed for research purposes.

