## **CHARACTERISTICS OF THE SUBJECT POPULATION**

### **4. Accrual**

**Is this study conducted solely at sites under the oversight of the Joint Pediatric IRB (e.g. UNMC, TNMC, CH&MC, UNO)?**

Yes

**A. What is the total number of subjects (per group, as applicable) needed to complete the research in order to achieve the scientific objectives of the research?**

104 subjects are needed to complete the trial (52 per treatment group).

**B. What is the statistical or other justification for the total number of subjects needed to complete the research in order to achieve the scientific objectives of the research?**

The primary outcome is the change of Affective Reactivity Index (ARI) from the baseline to the last visit. A sample size of n=52 per group will provide 80% power to detect a difference between the group means of -4.0 in the change of ARI of -4.0 at the significance level of

0.05 using a two-sided two-sample t-test, assuming the mean of -4.0 and the standard deviation of 7.2 in the oxytocin group, and the mean of 0 and the standard deviation of 7.2 in the placebo group.

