**Neuroimaging:**

The clinical MRI scanning of brain will occur at the MRI visit 1, to rule out any anatomical abnormality of the participants brain, such as brain tumor, hemorrhage, or other structural abnormality. This will occur at the Boys Town National Research Hospital. During the MRI visit 1, participants will receive their first fMRI session immediately before initiation of oxytocin or placebo treatment. The fMRI visit 1 can happen on the same day of the initial research assessment after the initial research assessment is completed.

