### **Oxytocin/placebo administration**

If the participants are assigned to the oxytocin treatment arm by randomization, they will be initiated on oxytocin administration after the MRI visit 1 and MEG visit 1. Following previous studies using intranasal oxytocin administration (Dadds et al., 2014; Guastella & MacLeod, 2012; MacDonald et al., 2011), subjects weighing >40kg will receive a total of 24 IU of oxytocin delivered as 2-6 IU puffs to each nostril once daily. Subjects weighing <40kg will receive a total of 12 IU of oxytocin delivered as 1-6 IU puff to each nostril daily. Participants will receive 14 to 21 days of daily oxytocin/placebo administration. After 14 days of oxytocin/placebo administration, participants will be scheduled to have MRI visit 2 and MEG visit 2. After those two visits are completed, participants will stop oxytocin/placebo administration. Participants who are assigned to placebo treatment branch will receive identical bottles and instructions for delivery of all the other ingredients of nasal spray except oxytocin. The instruction and demonstration will be given to the parents or parent/legal guardian as the first administration of the nasal spray done at the clinic by either child and adolescent psychiatrist or advanced practice registered nurse. The daily administration will be done by dispatching either oxytocin or placebo nasal spray to the parents of the participants. The oxytocin and placebo nasal spray will be prepared by the University of Nebraska Medical Center research pharmacist who will be un-blinded to each subject's treatment assignment. The randomization will be done by the department of pharmacology by a computer-programmed randomization procedure.

The participants will have one or two weekly visits to the clinic, depending on the duration of the trial (one if it is 14 days, 2 if it is more than 14 days and less than 21 days). If the participant is having two weekly visits, the first will be conducted by phone. They will be assessed for symptom level, nasal spray tolerance, and assessment of adverse effects. Participants will be initiated on psychiatric treatment if it is indicated by change of their psychiatric condition (such as worsening of psychiatric symptoms). In this case, they will be

withdrawn from the study.

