### **Statistical methods for the internal pilot study**

The first 20 patients will be enrolled and randomly assigned into placebo and oxytocin group. The primary outcome ARI will be measured at the baseline and last visit for each patient. The change of ARI will be calculated as the measure at the last visit minus the measure at the baseline for each patient. The treatment status of each patient will be labeled as A and B by the third party, and all persons associated with the internal pilot study will be kept blinded for group assignment. The SD of the change of ARI will be estimated for each intervention group, and will be used to compute the pooled SD for the internal pilot study. Recalculation of the sample size will be performed using a two sample independent t-test and the pooled SD. The retention rate will be assessed as well.

The data on genetic polymorphisms and OT-treatment outcomes on the neural and psychological measures will be used primarily as pilot data to advise future larger-scale studies. OXTR SNPs vary in frequency in western populations, but there should be sufficient exemplars of varying genotypes to allow preliminary analyses. For example, a commonly-identified OXTR SNP associated with variation in social behavior (rs53576) occurs in frequencies of 53.5% and 46.5% for the risky genotype (A/A and A/G) relative to resilient genotype (G/G) in a Caucasian sample (Jacob et al., 2007).

Finally, we will simultaneously test all measures (e.g., at baseline) in a multivariate analysis to determine the most important measures for predicting outcome in terms of behavioral change (Ecker et al., 2010). It is hoped that this will show which ones of the variables are the best predictors of treatment response, and which aspects are best influenced by treatment.

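### The only pre-dose ARI is both the entry test and the primary baseline, with no limit on its lag to first dose; a second pre-dose reading, averaged in, would add some power cheaply

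*Combined protocol and SAP*

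**What the plan says.** **Outcome and test.** Section 4.B: "The primary outcome is the change of Affective Reactivity Index (ARI) from the baseline to the last visit". Section 12.F, on the internal pilot, defines the score: "The change of ARI will be calculated as the measure at the last visit minus the measure at the baseline for each patient". Section 12.F compares the arms by a two-sample t-test on change. Its ANCOVAs concern change in BOLD response and do not adjust ARI for its baseline.

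**ARI schedule.** Section 12.B, Evaluations: "These evaluation measurements will be administered at the initial research assessment session as well as the final research assessment session". The Symptom Profile Assessment text names the same two occasions for the ARI. Section 9 requires a score of at least 4, and section 12.A lists the ARI in the eligibility work-up. No other pre-dose ARI is scheduled, so the qualifying occasion is also the baseline.

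**Timing of first dose.** Section 12.B says of participants allocated to oxytocin that "they will be initiated on oxytocin administration after the MRI visit 1 and MEG visit 1". On the first scan: "The fMRI visit 1 can happen on the same day of the initial research assessment after the initial research assessment is completed". MEG visit 1 may also fall on that day. Same-day scanning is allowed, not required, and no maximum interval from ARI to first dose appears. The first fMRI is placed directly before treatment starts, so the imaging baseline is tied to dosing while the ARI baseline is not. The first spray is given at the clinic under supervision, with no ARI scheduled there.

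**Sample size.** Section 4.B: "A sample size of n=52 per group will provide 80% power to detect a difference between the group means of -4.0", tested at "0.05 using a two-sided two-sample t-test", with the placebo arm assumed to have a mean change of zero: "and the mean of 0 and the standard deviation of 7.2 in the placebo group".

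**The concern.** A single reading that must reach a threshold to admit a child tends to be high partly by chance. Using the same reading as baseline has two consequences. Its noise goes undiminished into the change score, which is what the t-test analyses. The expected change in an untreated child also drifts below zero, because the selected reading tends to regress towards that child's usual level. An open-ended gap before the first dose can make the baseline less representative of the child's state when treatment begins.

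At stake are efficiency of the primary test and interpretation of within-arm change. Section 18.G, for instance, considers termination if symptoms worsen or do not change after 10 patients per arm, and regression to the mean blurs that judgement. A supervised clinic contact already exists where a second 7-item form could be taken.

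**Working it through.** **Inputs from the plan.** Difference -4.0, SD of change 7.2 in each arm, 52 per group, two-sided alpha 0.05, t-test (4.B); change equals last visit minus baseline (12.F).

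**Assumed, not in the plan.** Equal variances at each occasion; r, the correlation of a pre-dose reading with the final reading; rb, the correlation between two pre-dose readings.

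**Step 1: reproduce the stated power.** Noncentrality = 4.0 / (7.2 × √(2/52)) = 2.83, on 102 degrees of freedom. Power is 80.1%, and 52 is the smallest n per group that reaches 80%. The figure reproduces.

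**Step 2: baseline as the mean of two pre-dose readings.** In units of the variance of one reading, the variance of change is 2 - 2r with one baseline reading and 1 + (1 + rb)/2 - 2r with the mean of two. The ratio is [1 + (1 + rb)/2 - 2r] / (2 - 2r), and the new SD is 7.2 × √ratio. With r = 0.5:

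| rb | Ratio | SD of change | Power at 52 per group | n per group for 80% |
|---|---|---|---|---|
| 0.5 | 0.750 | 6.24 | 90.0% | 40 |
| 0.7 | 0.850 | 6.64 | 86.1% | 45 |
| 0.8 | 0.900 | 6.83 | 84.1% | 47 |
| 0.9 | 0.950 | 7.02 | 82.1% | 50 |
| 0.95 | 0.975 | 7.11 | 81.1% | 51 |
| 1.0 | 1.000 | 7.20 | 80.1% | 52 |

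When rb = r the ratio is 0.75 whatever r is. With rb = 0.95 and r from 0.3 to 0.7, power is 81-82%. The working range is therefore about 81-90%.

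**Step 3: allow for selection on the first reading.** A normal-model simulation (2 million draws) used an entry cut from 1 SD below to 1 SD above the mean, r of 0.5 or 0.7, and rb equal to r or halfway between r and 1. Averaging gave 82-89% power. Mean change without any treatment effect was -0.09 to -0.76 SD of one reading from the single baseline, and -0.04 to -0.57 SD from the averaged one. Averaging reduces regression to the mean but does not remove it.

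**Step 4: other uses of a second reading.** Replacing the first reading with the second leaves power at 80.1% if both correlate equally with the final reading, and gives 71-78% in the selection model. It helps only if the later reading tracks the final one better: r rising from 0.5 to 0.6 gives 88%, ignoring selection. Change from the second reading with the first as covariate has ratio [2 - 2r - (r - rb)²] / (2 - 2r). At r = 0.5 and rb = 0.5 / 0.7 / 0.8 / 0.9 that is 1.00 / 0.96 / 0.91 / 0.84, for power of 80.1 / 81.7 / 83.7 / 86.5%.

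**Step 5: ANCOVA, ignoring selection.** Adjusting for the existing single ARI has ratio (1 - r²) / (2 - 2r). At r = 0.5 this is 0.75 / 1 = 0.75, so SD 6.24 and power 90.0%. At r = 0.3 and 0.7 power is 93.6% and 86.1%. Adjusting for the mean of two readings has ratio [1 - 2r²/(1 + rb)] / (2 - 2r). At r = 0.5 and rb = 0.5 / 0.7 / 0.8 / 0.9 power is 93.0 / 91.6 / 91.0 / 90.5%. The one degree of freedom spent on the covariate is ignored here.

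**The case against.** Change from one pre-treatment reading is ordinary design, and nothing here contradicts another part of the plan. The SD of 7.2 is stated for the change itself, so single-baseline noise is already within it. This stands: power is lower only in comparison with a better design.

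The more efficient remedy is analytic. At r = 0.5, ANCOVA on the existing reading matches the best case for averaging with no extra form; once ANCOVA is used, a second reading adds only about 0.5 to 3 percentage points. This also stands, and it belongs in the recommendation.

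The gain depends on separation in time. Both first scans may fall on the assessment day, and section 23 foresees only 3-5 visits in all. If the two readings are hours apart, rb approaches 1 and the gain approaches zero. The 90% case needs two pre-dose readings to agree no better than readings before and after 14-21 days of treatment, which is the favourable extreme.

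Nor is n fixed. The internal pilot recalculates it from the pooled SD of the first 20 patients, so a smaller SD may give a smaller trial instead of more power.

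A reader might go further and infer that regression to the mean biases the treatment effect, that the trial falls short of 80% power, or that a non-zero placebo change undermines the sample size. The documents support none of these. Regression acts on both randomised arms alike, the 80% reproduces, and power depends on the -4.0 difference, not on either arm's mean. Even the claim that a placebo mean of 0 cannot hold is too firm, because the plan gives no ARI distribution to show how strongly a cut of 4 selects.

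**Conclusion.** The point holds as a low-cost improvement, not as an error in the plan. One pre-dose ARI occasion serves as both qualifier and baseline, and its lag to first dose is unbounded. The comparison is unbiased and the planned power is correct on its own inputs. A placebo mean change of 0 is unlikely, but that affects the reading of within-arm change rather than power.

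Averaging a second pre-dose reading would lift power of the planned t-test from 80% to about 81-90% at 52 per group. Equivalently, it would reduce the n for 80% power to between 51 and 40 per group. These figures assume equal variances and correlations the plan does not supply. ANCOVA on the single existing reading gives about 90% at r = 0.5, and combining the two gives about 90-93%.

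One ambiguity bears on this: the ARI has self-report and parent-report versions, and the plan does not say which is the entry or primary score. A single reading here means a single occasion.

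**What to change.** 1. In 12.B, repeat the ARI at the supervised first-dose contact, before the spray.
2. Keep the initial-session ARI as the entry test. Define baseline as the mean of the two pre-dose readings in 4.B, in 12.F and in the internal-pilot SD, so that the recalculated n matches the score analysed.
3. Do not use the second reading alone as baseline, and do not use change from it with the screening reading as covariate. The first can lose power; the second gains little or nothing when the two readings correlate only modestly, and at r = 0.5 it falls below plain ANCOVA throughout the range shown.
4. State in 12.F whether ARI will be analysed by baseline-adjusted ANCOVA. That step needs no new data and would be the first choice if only one change were made. If adopted, the pilot recalculation should use the matching residual SD.
5. State a maximum interval from the initial ARI to first dose, and note that a same-day repeat adds little.

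The cost is one extra 7-item form at a contact that already takes place, a few minutes of family time per child, and protocol wording.

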**Initial evaluation:**

Participants and their parent/guardian will complete a diagnostic assessment session following informed consent. This will be held at the outpatient clinic of the department of psychiatry, at University of Nebraska Medical Center. Participants and their parent/guardian will be interviewed using the Schedule for Affective Disorders and Schizophrenia for School-Age Children-Present and Lifetime Version (K-SADS) (Kaufman et al., 1997) to confirm the diagnosis of ADHD/CD/ODD/DMDD, and to rule out any other psychiatric diagnoses listed in the exclusion criteria. K-SADS may be completed remotely by video call or phone. IQ will be measured by the Wechsler Abbreviated Scale of Intelligence, Second Edition (2-subtest form)(Wechsler, 2011). The WASI-II is standardized, well-established test for measurement of intelligence in adolescents population (David Wechsler, 2011). This will be used to rule out intellectual disability (I.Q. < 70)

**Symptom Profile Assessment:**

The Affective Reactivity Index (ARI) will be completed at the initial research assessment session and the final research assessment session. ARI is a 7 item inventory (self-report

and parent-report versions) specifically designed to measure irritability and emotional dysregulation (Stringaris et al., 2012). This will be used to measure the outcome of improvement in irritability by oxytocin treatment.

The Behavior Assessment System for Children, second version (BASC-3) will be completed at the initial research assessment session and the final research assessment session. BASC-3 is parent-reported, well-established scale for externalizing/internalizing problem of children and adolescents (Reynolds, 2015). This will be used to measure the outcome of improvement in emotional dysregulation and other related symptoms (externalizing behavior) by oxytocin treatment.

The Inventory of Callous Unemotional trait (ICU) will be completed at the initial research assessment session and the final research assessment session. ICU is a 24 item inventory specifically designed to measure callous-unemotional trait in children and adolescents (Berg et al., 2013; Frick, 2004). This will be used to measure outcome of improvement in callous-unemotional trait by oxytocin treatment. This will be also used to assess covariate function of callous-unemotional trait on treatment response.

The Reactive-Proactive Aggression Questionnaire (RPAQ) will be completed at the initial research assessment session and the final research assessment session. RPAQ is a 23 item inventory (self-report) specifically designed to measure two different types of aggressive behavior, i.e., reactive and proactive aggression (Raine et al., 2006). This will be used to measure outcome of improvement in related symptom of aggressive behavior by oxytocin treatment.

The Clinical Global Impression: Severity and Clinical Global Impression: Improvement scales (CGI-S and CGI-I) will be used at study entry and study completion to quantify, based on clinician's global assessment of the individual, the severity of symptoms compared (study entry and completion) and the degree of improvement (study completion) which may or not be attributable to the study intervention. Other symptom profile measurements will be used to assist the clinician in the rating of this measure.

Children's Global Assessment Scale (CGAS) will be used at study entry and completion to provide a global measure on a scale of 0-100 (100 being superior) of the subject's level of functioning.

**Urine drug screen:** Urine drug screen to rule out presence of substances of abuse will be completed at screening.

**Urine pregnancy testing:** Urine test for pregnancy will be done for female participants prior

to initial neuroimaging procedures.

**Neuroimaging:**

The clinical MRI scanning of brain will occur at the MRI visit 1, to rule out any anatomical abnormality of the participants brain, such as brain tumor, hemorrhage, or other structural abnormality. This will occur at the Boys Town National Research Hospital. During the MRI visit 1, participants will receive their first fMRI session immediately before initiation of oxytocin or placebo treatment. The fMRI visit 1 can happen on the same day of the initial research assessment after the initial research assessment is completed.

Participants will be scanned on the 3.0 Tesla Philips scanner at Boys Town National Research Hospitals Radiology Department. If the child or parent prefers, the parent is welcome to stay with the child during the MRI scan. Pregnancy test will be done on all female participants, using urine sample collected no more than 24 hours before the scan. The participant will be escorted to the MRI scanner room. They will be given the instruction of the fMRI scanning procedure and neuropsychological tasks they will be performing in the scanner, by an MRI technician. Practice runs of neuropsychological tasks will be done, so the participant will become familiar with the tasks. After checking once more that the participant doesn't have any contra-indication to the MRI scanning, including metal objects, they will be escorted in to the MRI scanning room. Ear plugs will be placed by the MRI technician to mitigate the noise from the MRI machine. The MRI technician will guide the participant lying down on the bed of the scanner, and make sure they can see the mirror for the neuropsychological tasks, and also feel comfortable with the scanner. Instruction will be given that the participant needs to stay still. Once the participant is ready, the bed the participant is lying on will be guided into the magnetic coil field. The microphone will be checked once the participant is in the magnetic coil field, to make sure the participant can hear the MRI technician, and also the MRI technician can hear the participant. Two fMRI tasks will be used: the affective Stroop, and the fearful expression. If the participant has never received MRI scanning of brain before, a clinical scanning of brain will be included to detect any potential anatomical abnormality. After they finish the neuropsychological tasks and anatomical scanning (~ 1 hour), they will be guided to the outside of the scanner. Post-scanning questionnaire will be filled to check if the participant performed the neuropsychological tasks well without difficulty, or had any event to report (such as feeling uncomfortable inside of the scanner). Total scan time is under 1 hour and total time for the visit will be under 2 hours. All these steps will be conducted at Boys Town National Research Hospital, the department of radiology.

***The Fearful Expression Processing task***

This is a shortened version of the paradigm previously utilized by our group (Marsh & Blair,

2008). During each trial the participant is asked to decide the gender of the face displayed. The face either demonstrates neutral affect or a morphed intensity of fear (50%, 100% or 150%). A trial involves: the presentation of a face (1500 ms) and then a fixation point (1000 ms). There is one run of this task, with 120 face trials (30 neutral, 30 50% fear, 30 100% fear and 30 150% fear) and 60 fixation point trials. In addition, there are 15 seconds of fixation point trials at the beginning and end of the run. Task duration is 8 minutes.

### ***The Affective Stroop task***

The affective task used here was an adapted version of the paradigm described in previous work (K. S. Blair et al., 2012; K. S. Blair et al., 2007). During each trial the participant is asked to decide how many numbers are displayed on the screen, instead of the value of the number. For congruent trials, the numbers were displayed with the same numerosity and number value (e.g., three 3s). For incongruent trials, the numbers were displayed with different numerosities and number values (e.g., four 3s). The individual numerical stimuli consisted of three, four, five, or six 3s, 4s, 5s, or 6s randomly presented within a 9-point grid. There are an equal number of congruent trials and incongruent trials (48 each for a run). These number pictures were preceded and followed by emotional stimuli pictures consisting of 48 positive, 48 negative, and 48 neutral pictures selected from the International Affective Picture System. A trial involves: the presentation of an emotional stimuli (400ms), a numerical display (400ms), the same emotional stimuli (400ms), and a blank (1300ms). Subject completed two runs, generating 288 picture-trial events (32 in each 9 categories) and 96 fixation points to generate a baseline.

The first MEG scan (MEG visit 1) will take place at the Center for MEG ([name]) on the day of their scheduled study. The MEG visit 1 can happen on the same day of the initial research assessment.

The participant will be escorted to the prep station inside the MEG suite by the MEG technician for MEG coil placement and further prepping prior to the study. The coils are simply small discs that are attached to the skin surface. After coils are placed, they will be lead into the magnetically shielded room, which houses the MEG system, and positioned by the MEG technician. Once positioned, the MEG technician will go over the instructions a second time to make sure the subject understands and has not forgotten items discussed during the consent process (e.g., to remain physically still). The MEG technician will then close the door to the magnetically-shielded room, walk to the acquisition workstation and test the intercom system by asking the participant a question (e.g., Can you hear me?) The MEG technician will then tell the participant we are ready to begin and remind them to stay very still. MEG data will then be acquired by the technician as the subject completes the behavioral task. The recording will last less than 10 minutes. The participant will then be informed via intercom that the scan is over and they can relax. After 3-5 minutes break, the

participant will be told we are ready to start again and the process of recording will be repeated as the participant performs another set of behavioral task. Once all of the tasks have been completed (~1 hour), the MEG technician will inform the subject they are finished and he/she will enter the room to lead them out into the MEG suite. Once outside the magnetically-shielded room, the MEG technician will remove the MEG coils from the participant and allow them to use the private bathroom with cleansing station to touch up their make-up and/or fix their hair (i.e., the MEG helmet typically flattens ones hair). He/she will then be able to pick up any of their belongings (e.g., purse) that was stored in the MEG participant lockers.

